8.4.6.3 Follow-up of Adverse Events and Serious Adverse Events

After the initial adverse event/serious adverse event report, the investigator is required to proactively follow each subject at subsequent visits/contacts. All adverse events and serious adverse events will be followed until resolution, stabilization, until the event is otherwise explained, or the subject is lost to follow-up (as defined in Section 7.3).

Further information on follow-up procedures is given in Section 11.4.

All new information for previously reported serious adverse events must be sent to Amgen immediately and no later than 24 hours following awareness of the new information. If specifically requested, the investigator may need to provide additional follow-up information, such as discharge summaries, medical records, or extracts from the medical records. Information provided about the serious adverse event must be consistent with that recorded on the Events CRF.

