 - Dates of onset and resolution (if resolved);
 - Did the event start prior to first dose of investigational product
 - Assessment of seriousness;
 - Severity (or toxicity defined below);
 - Assessment of relatedness to investigational product(s), noninvestigational products/auxiliary medicinal product(s)
 - Assessment of relatedness to study-required activity and/or procedures is only required for Serious Adverse Events
 - Action taken; and
 - Outcome of event.
- It is not acceptable for the investigator to send photocopies of the subject's medical records to sponsor in lieu of completion of the Events CRF.
- If specifically requested, the investigator may need to provide additional follow-up information, such as discharge summaries, medical records, or extracts from the medical records. In this case, all subject identifiers, with the exception of the subject number, will be blinded on the copies of the medical records before submission to Amgen.
- The investigator will attempt to establish a diagnosis of the event based on signs, symptoms, and/or other clinical information. In such cases, the diagnosis (not the individual signs/symptoms) will be documented as the adverse event/serious adverse event.

Evaluating Adverse Events and Serious Adverse Events

Assessment of Severity

The investigator will make an assessment of severity for each adverse event and serious adverse event reported during the study. The assessment of severity will be based on:

The Common Terminology Criteria for Adverse Events (CTCAE), version 5.0, which is available at the following location:

http://ctep.cancer.gov/protocolDevelopment/electronic_applications/ctc.htm.

with the following exceptions: Cytokine release syndrome and ICANS will be graded according to American Society for Transplantation and Cellular Therapy (ASTCT) (Lee et al, 2019).

Assessment of Causality

- The investigator is obligated to assess the relationship between investigational product(s), noninvestigational products/auxiliary medicinal product(s) and each occurrence of each adverse event.
- The investigator is obligated to assess the relationship between investigational products, noninvestigational products/auxiliary medicinal product(s, study-required activity, and/or procedure(s), and each occurrence of each serious adverse event.
- Relatedness means that there are facts or reasons to support a relationship between investigational product and the event.

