**Duration of Adverse Event**

$$\text{Duration of resolved adverse events (days)} = (\text{event end date} - \text{event start date}) + 1$$

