### Time to Adverse Event Resolution

Time to resolution is defined as the interval from the event start date to event end date. Unresolved events are censored at last dose of tarlatamab date + 65 days, end of study date, death date or analysis cutoff date, whichever occurs earlier.

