**5.4 Analysis Methods****5.4.1 General Considerations**

Descriptive statistics will be provided for exposure and safety endpoints. Descriptive statistics on continuous data will include means, medians, standard deviations, Q1, Q3, minimum, and maximum; while categorical data will be summarized using frequency counts and percentages. For time to safety event variables, Kaplan-Meier (KM) estimates and corresponding two-sided 95% confidence interval will be provided.

Data derivation from each study will follow their own principles specified in the individual study SAPs.

Imputation for missing or incomplete data may be performed if required. Incomplete adverse event and death dates will be imputed as described in Appendix A.

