Additionally, summaries of time to first onset of treatment-emergent EOIs from first tarlatamab administration (days), time to first onset of treatment-emergent EOIs after each dose from last prior tarlatamab administration (days), and duration of treatment-emergent EOIs (days) will be provided. Summaries of time to first onset of treatment-emergent EOIs from first tarlatamab administration (hours), and time to first onset of treatment-emergent EOIs after each dose from last prior tarlatamab administration (hours) will be provided for CRS (AMQ Narrow) only. Summaries of treatment-emergent CRS (AMQ Narrow) by dose, time from onset of grade 1 treatment-emergent CRS (AMQ Narrow) to grade 2 or higher treatment-emergent CRS (AMQ Narrow) by dose, time from onset of grade 1 treatment-emergent CRS (AMQ Narrow) to grade 2 treatment-emergent CRS (AMQ Narrow), duration of treatment-emergent CRS (AMQ Narrow) for participants that required tocilizumab, participant incidence of treatment-emergent CRS (AMQ Narrow) treated with tocilizumab, participant incidence of recurrent treatment-emergent CRS (AMQ Narrow), summary of treatment-emergent CRS (AMQ Narrow) rebound incidence in participants following recommended tarlatamab dosage for restarting therapy after dose delay, participant incidence of intervention utilization in relation to treatment-emergent CRS (AMQ Narrow), participant incidence of intervention utilization within and after 24 hours of last prior dose at cycle 1 day 1 and cycle 1 day 8 for grade 2 or higher treatment-emergent CRS (AMQ Narrow), participant incidence and time to onset for grade 2 or higher treatment-emergent CRS (AMQ Narrow) by dose will be presented, other analyses for CRS (AMQ Narrow) may be provided as well if needed. Participant incidence of treatment-emergent ICANS and associated neurological events by last prior tarlatamab administration, participant incidence of treatment-emergent ICANS and associated neurological events by last prior tarlatamab administration visit and worst grade, participant incidence of recurrent treatment-emergent ICANS and

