associated neurological events, **summaries of time to first onset of treatment-emergent ICANS from first tarlatamab administration (days), time to first onset of treatment-emergent ICANS after each dose from last prior tarlatamab administration (days), and duration of treatment-emergent ICANS (days)** will be presented. Summaries of time to onset of treatment-emergent EOIs and duration of treatment-emergent EOIs will be provided for grade 2 or higher and grade 3 or higher treatment-emergent EOIs respectively.

Listing of recurrent treatment-emergent CRS (AMQ Narrow) will be produced with all the relevant fields.

Overall summary of treatment-emergent CRS (AMQ Narrow) and treatment-related treatment-emergent CRS (AMQ Narrow), time to first onset of treatment-emergent CRS (AMQ Narrow) from first tarlatamab administration (days), time to first onset of treatment-emergent CRS (AMQ Narrow) after each dose from last tarlatamab administration (days and hours), duration of treatment-emergent CRS (AMQ Narrow) (days), treatment-emergent CRS (AMQ Narrow) by dose, time from onset of grade 1 treatment-emergent CRS (AMQ Narrow) to grade 2 or higher treatment-emergent CRS (AMQ Narrow) by dose, time from onset of grade 1 treatment-emergent CRS (AMQ Narrow) to grade 2 treatment-emergent CRS (AMQ Narrow), **and participants incidence of hospitalization due to treatment-emergent CRS (AMQ Narrow) during cycle 1 day 1 and cycle 1 day 8 doses by grade** among participants who received tarlatamab and were enrolled from monotherapy cohorts of study 20160323 part F and tarlatamab arm of study 20210004 under PA3 with mandatory 6 to 8 hours monitoring post-infusion at cycle 1 day 1 and cycle 1 day 8 and participants who received tarlatamab with more than mandatory 6 to 8 hours monitoring post-infusion at cycle 1 day 1 and cycle 1 day 8 may be summarized side by side if there is sufficient number of participants, other analyses for CRS (AMQ Narrow) may be provided as well if needed.

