**Table 4. Imputation Rules for Partial or Missing Start Dates**

Start Date		Stop Date						missing	
		Complete: yyyymmdd		Partial: yyyymm		Partial: yyyy			
		< 1 st dose	≥ 1 st dose	< 1 st dose yyyymm	≥ 1 st dose yyyymm	< 1 st dose yyyy	≥ 1 st dose yyyy		
Partial: yyyymm	= 1 st dose yyyymm	2	1	2	1	n/a	1	1	
	≠ 1 st dose yyyymm		2		2	2	2	2	
Partial: yyyy	= 1 st dose yyyy	3	1	3	1	n/a	1	1	
	≠ 1 st dose yyyy		3		3	3	3	3	
Missing		4	1	4	1	4	1	1	

1 = Impute the date of first dose

2 = Impute the first of the month

3 = Impute January 1 of the year

4 = Impute January 1 of the stop year

Note: For participants who were never treated (first dose date is missing), partial start dates will be set to the first day of the partial month.

Note: If the start date imputation leads to a start date that is after the stop date, then do not impute the start date.

Imputation rules for partial or missing stop dates:

- For partial stop date mm-yyyy, impute the last of the month.
- For partial stop date yyyy, impute December 31 of the year.
- For completely missing stop date, do not impute.
- If the stop date imputation leads to a stop date that is after the death date, then impute the stop date as the death date.

- If the stop date imputation leads to a stop date that is before the start date, then there is a data error and do not impute the stop date. (ie. set the stop date as missing).

Imputation rules for partial or missing death dates:

- If death year and month are available but day is missing:
  - If mmYYYY for last contact date = mmYYYY for death date, set death date to the day after the last contact date.
  - If mmYYYY for last contact date < mmYYYY for death date, set death date to the first day of the death month.
  - If mmYYYY for last contact date > mmYYYY for death date, data error and do not impute.
- If both month and day are missing for death date or a death date is totally missing, do not impute.

Note that the last contact date refers to the last contact (i.e. a visit or an assessment) with participant instead of family members. Last contact date would be derived from the latest participant visit/assessment date.

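### Duration of events of interest is defined for resolved events only, so the summaries omit unresolved events and probably understate duration; the censored alternative is named in no output, and its day-65 cap can precede a late onset

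*SAP*

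**What the plan says.** iSAP Section 3 defines duration as end date minus start date plus 1, under the label "Duration of resolved adverse events (days". Appendix A completes partial stop dates, but says: "For completely missing stop date, do not impute".

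The protocol shows how an event can lack a stop date. Appendix 4 (Section 11.4) has sites record "Dates of onset and resolution (if resolved", and Section 8.4.6.3 says events "will be followed until resolution, stabilization, until the event is otherwise explained, or the subject is lost to follow-up". An event that stabilises, or whose patient is lost, can leave follow-up without an end date.

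Duration is then requested widely. iSAP Section 5.4.4.2 states that "duration of treatment-emergent EOIs (days) will be provided", asks separately for CRS and ICANS, and adds that "duration of treatment-emergent EOIs will be provided for grade 2 or higher and grade 3 or higher treatment-emergent EOIs respectively". Section 5.5, written for an FDA postmarketing requirement, asks for the duration of EOIs and of serious EOIs in four periods, and for pituitary dysfunction in Periods 3 and 4. None of these outputs says what happens to an unresolved event.

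Section 3 also defines Time to Adverse Event Resolution: "Unresolved events are censored at last dose of tarlatamab date + 65 days, end of study date, death date or analysis cutoff date", whichever is earliest. Section 5.4.1 adds a general sentence: "For time to safety event variables, Kaplan-Meier (KM) estimates and corresponding two-sided 95% confidence interval will be provided".

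**The concern.** Events still open when observation stops tend to be the long ones, so a summary restricted to closed events tends to run short. These durations go into the safety summary for the second-line filing and into the postmarketing characterisation of CRS and ICANS. The issue matters most for events that can persist, such as neurological or pituitary events, and in the late periods of Section 5.5.

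No listed summary counts the events left out. Section 5.5 refers to Section 5.4.4.2 for outcome. That section covers fatal events, discontinuation and CRS hospitalisation, but gives no number unresolved.

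The censored variable would address this, but it is tied to no named output, and its cap was not written with Period 4 in mind. Period 4 begins when safety follow-up ends.

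**Working it through.** The plan states no figure for duration or for the share unresolved, so there is nothing to reproduce. Items 1 and 2 illustrate the omission on stated assumptions. Item 3 uses dates from the documents.

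**1. Mean, two-group arithmetic.** Let u be the share unresolved and r the true duration of unresolved events divided by that of resolved events (both assumed). Then resolved-only mean / mean of all events = 1 / (1 + u(r - 1)). For u = 0.10 and r = 3 this is 1 / 1.20 = 0.833, or 16.7% too low.

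| u | r = 1.5 | r = 2 | r = 3 |
|---|---|---|---|
| 0.01 | 0.5% low | 1.0% low | 2.0% low |
| 0.05 | 2.4% low | 4.8% low | 9.1% low |
| 0.10 | 4.8% low | 9.1% low | 16.7% low |
| 0.20 | 9.1% low | 16.7% low | 28.6% low |

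The direction depends on r. With u = 0.20 and r = 0.5 the ratio is 1 / 0.90 = 1.11, so the resolved-only mean would be 11% too high.

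**2. Median, censoring model.** Assume exponential durations (resolution rate λ) and independent exponential censoring (rate μ). The share unresolved is u = μ / (λ + μ), and resolved events follow an exponential with rate λ + μ. Their mean and median therefore equal the true values times (1 - u). A simulation of 400,000 events with an assumed true mean of 30 days (true median 30 × ln 2 = 20.8) gave:

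| u | Resolved-only median (days) | Kaplan-Meier median (days) |
|---|---|---|
| 0.02 | 20.33 | 20.75 |
| 0.05 | 19.79 | 20.86 |
| 0.10 | 18.69 | 20.78 |
| 0.20 | 16.67 | 20.84 |
| 0.40 | 12.47 | 20.77 |

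Keeping unresolved events as censored recovers the true median; dropping them understates it by about u. The two models agree. In the second, r = (2 - u) / (1 - u), which is 1.8 / 0.8 = 2.25 at u = 0.20, and the first formula then gives 1 / (1 + 0.20 × 1.25) = 0.80 = 1 - u.

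**3. The cap.** Protocol Section 8.1.4 puts the safety follow-up visit at about 60 (+5) days after last dose, so in study 20210004 Period 4 starts at about day 60 to 65. Section 8.4.6.1.3 still has related serious events reported after that. The longest censored time an unresolved event can contribute is 65 minus its onset day, both counted from last dose:

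| Onset day | 60 | 65 | 66 | 90 | 365 |
|---|---|---|---|---|---|
| Maximum censored time (days) | 5 | 0 | -1 | -25 | -300 |

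The definition states no +1. Adding one would turn -25 into -24 and would not change the conclusion.

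**The case against.** The strongest reply is that the plan already contains the remedy. Time to resolution is defined with explicit censoring, and the general Kaplan-Meier sentence in Section 5.4.1 can fairly be read to cover it. On that reading the gap is a missing cross-reference. This partly stands: a reader should not infer that the iSAP has no method for unresolved events. But no output in Section 5.4.4.1, Table 3, Section 5.4.4.2 or Section 5.5 names the variable, and the outputs that ask for duration would still follow the resolved-only definition.

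A reader might also infer that omitting unresolved events can only shorten duration. The documents do not show this. The r = 0.5 case above reverses the sign, so likely is the right word.

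Nor do the documents show that unresolved events are invisible. Section 5.4.4.1 plans a listing of treatment-emergent events with the relevant fields, which may identify them one by one. What is missing is a count in a summary.

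The cap alters no listed Period 4 output today, because Section 5.5 asks for duration rather than time to resolution. Day 65 also matches the end of the safety follow-up window in 20210004. The cap becomes a defect only if the variable is used for late onsets. The day 60 to 65 link is shown for 20210004 alone, because the other pooled studies' definitions are in SAPs that were not supplied. Those SAPs and the table shells may also say more about ongoing events.

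**Conclusion.** The point holds in a limited form. Following the text, the EOI duration summaries drop unresolved events and are likely, not certain, to understate duration. The size cannot be determined from the documents. Every percentage above rests on an assumed unresolved share and either an assumed duration ratio or an assumed censoring model. For CRS the effect is probably small (also an assumption); for EOIs that persist it could be larger.

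The cap result is exact arithmetic, but conditional: it applies to unresolved events starting after last dose + 65 days, and only if the censored variable is used for them.

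The iSAP is descriptive and tests no hypothesis, so no error rate is affected. The change is still worth making, because it uses a variable already defined and makes the omission visible.

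**What to change.** (a) Beside each EOI duration summary in iSAP Sections 5.4.4.2 and 5.5, report Kaplan-Meier time to resolution from the variable already defined in Section 3, together with the number of unresolved events. Label the existing measure as duration among resolved events.

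(b) State that a censoring date never precedes onset. For events starting after last dose + 65 days, replace that cap with the last date the event was known to be ongoing, no later than end of study, death or analysis cutoff. Using the last known date matters because follow-up may stop at stabilisation; censoring at end of study would count unobserved time as unresolved. State also that an event ending in death is not counted as resolved, since the contingency report form instructions in protocol Appendix 4 enter the date of death as the end date of a fatal event.

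Cost: a few sentences and a little more programming. Event outcome is already a mandatory adverse event attribute in protocol Appendix 4, so counting unresolved events needs no new data; for late events the last known ongoing date has to be taken from existing follow-up records. Kaplan-Meier medians may not be reached for EOIs with many unresolved events.

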**Exposure-Adjusted Event Rate of TEAE**

Exposure-adjusted event rate will be calculated as:

$$(\text{Total number of TEAEs}) / (\text{total participant years of exposure of tarlatamab}) * 100$$

**Fridericia-corrected QT Interval (QTcF):**

The Fridericia correction will be calculated from the investigator reported QT (ms) and RR interval (ms) if available, as follows:

$$QTcF = QT / (RR/1000)^{0.33}$$

QTcF will be only summarized if RR is collected.

**Long Term Follow-Up**

Each study will follow their own definition, which are specified in the individual SAPs.

**Relative Dose Intensity**

Relative dose intensity (%) is calculated as (actual cumulative dose / planned cumulative dose)\*100, where

- Actual cumulative dose is the total dose of tarlatamab given up to the data cutoff. For participants who did not take any drug the actual cumulative dose is 0 mg.
- Planned cumulative dose is the planned dose of tarlatamab accumulated over the actual duration on study treatment.

### Safety Follow-Up

Each study will follow their own definition, which are specified in the individual SAPs.

### Study Day

Post study day: study day = (date - date of study day 1) + 1

Pre-study day: study day = (date – date of study day 1)

### Study Day 1

Study day 1 is defined as the first day that any of tarlatamab or other protocol-required therapies is administered to the participant.

### Time to Adverse Event Resolution

Time to resolution is defined as the interval from the event start date to event end date. Unresolved events are censored at last dose of tarlatamab date + 65 days, end of study date, death date or analysis cutoff date, whichever occurs earlier.

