BPI-SF = Brief Pain Inventory - Short Form; C1D1 = cycle 1 day 1; C1D8 = cycle 1 day 8; C2D1 = cycle 2 day 1; CT = computed tomography; CTCAE = Common Terminology Criteria for Adverse Events; [REDACTED] ECG = electrocardiogram; ECHO = echocardiogram; ECOG PS = Eastern Cooperative Oncology Group Performance Status; EOI = end of infusion; EOT = end of treatment; EORTC-QLQ = European Organization for Research and Treatment of Cancer Quality of life Questionnaire; EQ5D-5L = 5-level EuroQoL - 5-Dimension; [REDACTED]; FACT-G = Functional Assessment of Cancer Therapy – General; FSH = follicle-stimulating hormone; FT4 = free T4; HIV = human immunodeficiency virus; ICANS - immune effector cell-associated neurotoxicity syndrome; IGF-1 = insulin like growth factor 1; LDH = lactate dehydrogenase; LH = luteinizing hormone; LSE = last subject enrolled; LTFU = long-term follow-up; MRI = magnetic resonance imaging; MUGA scan = multigated acquisition scan; PD = progressive disease; PGIC = Patient Global Impression of Change; PGs = Patient Global Impression of Severity; PK = pharmacokinetic; PRO-CTCAE = Patient-Reported Outcomes Version of the Common Terminology Criteria for Adverse Events; Q6W = every 6 weeks; SCLC = small cell lung cancer; SFU = safety follow-up; SoA = schedule of activities; SOC = standard of care; TSH = thyroid-stimulating hormone.

^a All procedures and assessments on dosing days are to be completed prior to study drug administration unless otherwise noted in the SoA.

^b On-study cycle 2 visits have a ± 2-day window and all subsequent visits beginning in cycle 3 will have a ± 3-day window, unless otherwise specified.

^c Safety Follow-up visit will occur approximately **60** (+ 5) days after last dose of study treatment.

^d Long-term Follow-up will occur every 12 weeks (± 14 days) from the SFU visit or last imaging visit, whichever is later. **Ad hoc vital status (survival status) collection may be required to support key study analysis.**

^e **Highly sensitive serum pregnancy test (for subjects of childbearing potential) at screening; serum or urine pregnancy test on day 1 of every cycle while receiving investigational product and then monthly following EOT until 60 days from the last tarlatamab dose.** Additional on-treatment pregnancy testing may be performed at the investigator's discretion if there is suspicion that a female subject is pregnant or per local laws and regulations.

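### The last dose + 65 day limit on time to adverse event resolution applies only to unresolved events, so a literal coding biases the late part of the resolution curve upward

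*SAP*

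**What the plan says.** The SAP, Section 3, under Time to Adverse Event Resolution, treats two kinds of event differently. For resolved events, "Time to resolution is defined as the interval from the event start date to event end date", with no limit on how late the end date may be. For the others, "Unresolved events are censored at last dose of tarlatamab date + 65 days, end of study date, death date or analysis cutoff date", taking the earliest of the four dates.

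Four other places bear on how this would be coded:

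- SAP Appendix A, on stop dates: "For completely missing stop date, do not impute". An event with no recorded end date therefore stays without one.
- SAP 5.4.1: "For time to safety event variables, Kaplan-Meier (KM) estimates and corresponding two-sided 95% confidence interval will be provided".
- Protocol 8.4.6.3: reported events "will be followed until resolution, stabilization, until the event is otherwise explained, or the subject is lost to follow-up".
- Protocol Schedule of Activities: "Safety Follow-up visit will occur approximately 60 (+ 5) days after last dose of study treatment". The top of that window is 60 + 5 = 65 days, which equals the SAP limit, although the SAP does not give this derivation.

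SAP 5.5 also defines a Period 4 that begins when safety follow-up ends, so the plan itself expects to use data from after that point.

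**The concern.** The natural coding is: end date present, count a resolution at its full time; end date missing, censor no later than last dose + 65 days. Under it, an event that resolves 120 days after the last dose counts as resolved at its full time. An event known to be still open at 120 days leaves the risk set at day 65. Whether an event remains at risk after the limit then depends on whether it resolves later. Kaplan-Meier assumes that censoring carries no information about the future outcome, and here it does.

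Any error favours the drug and falls on long-lasting events, for which a resolution curve is most informative. The integrated summary supports a second-line filing, and SAP 5.5 ties it to a postmarketing requirement to characterise CRS and ICANS further.

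**Working it through.** The documents give no resolution rate for this variable, so there is no planned figure to reproduce. The check compares three rules:

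- **Literal:** resolved events keep their full interval; unresolved events are censored by last dose + 65 days.
- **Common stop:** the limit applies to all events.
- **Full follow-up:** all events are followed to death or cutoff.

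**Step 1: worked example (assumed numbers).** 100 events start on the day of last dose and all are followed to day 180. By day 65, 60 resolve; 20 resolve on days 66 to 180; 20 stay open.

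- Truth at day 180: (60 + 20)/100 = 80%.
- Literal: S(65) = 1 − 60/100 = 0.40. The 20 open events are censored at day 65, leaving 20, all of which have end dates. Then S(180) = 0.40 × (19/20) × (18/19) × … × (0/1) = 0, so 100% resolved, an excess of 20 points.
- Common stop: 60% at day 65 and no estimate beyond it.
- Full follow-up: 80%.

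**Step 2: simulation by onset and speed (all inputs assumed).** 200,000 events per scenario; median last-dose day about 150; median death 180 days after last dose; cutoff between day 180 and day 900. With median resolution m days among events that resolve and a share p that never do, the truth is F(t) = (1 − p)(1 − 2^(−t/m)). For m = 90 and p = 0.2, F(90) = 0.8 × 0.5 = 40% and F(180) = 0.8 × 0.75 = 60%. The table shows truth → literal in percent; differences come from unrounded values.

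| Onset | m; p | Day 90 | Diff. | Day 180 | Diff. |
|---|---|---|---|---|---|
| Cycle 1 | 4; 0 | 100.0 → 100.0 | 0.0 | 100.0 → 100.0 | 0.0 |
| Cycle 1 | 30; 10% | 78.7 → 79.0 | +0.2 | 88.6 → 89.8 | +1.2 |
| Cycle 1 | 90; 20% | 40.0 → 40.4 | +0.4 | 60.0 → 62.9 | +2.9 |
| Spread over treatment | 30; 10% | 78.7 → 79.4 | +0.6 | 88.6 → 91.9 | +3.3 |
| Spread over treatment | 90; 20% | 40.0 → 41.0 | +1.0 | 60.0 → 67.1 | +7.1 |
| 30 days before to 60 days after last dose | 30; 10% | 78.7 → 85.8 | +7.0 | 88.6 → 99.0 | +10.4 |
| 30 days before to 60 days after last dose | 90; 20% | 40.0 → 51.5 | +11.5 | 60.0 → 85.6 | +25.6 |

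Full follow-up matched the truth within about 0.3 point throughout. The common stop did so wherever events remained at risk.

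**Step 3: mixtures of short and slow events (assumed).** About 400,000 events; treatment median 5 months, inside the protocol's 4 to 6; onset uniform on treatment; survival after stopping with median 7 months; cutoff 6 to 24 months; short events with median 0.7 month. Results at 12 months:

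- 30% slow, median 12 months: truth 0.70 + 0.30 × 0.5 = 85.0%; literal 92.8%; excess 7.8 points.
- 50% slow, median 12 months: truth 0.50 + 0.50 × 0.5 = 75.0%; literal 87.5%; excess 12.5 points.
- 30% slow, median 24 months: truth 0.70 + 0.30 × (1 − 2^(−0.5)) = 78.8%; literal 87.4%; excess 8.6 points.

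At 6 months the excess was 3.5 to 4.8 points. Only 4 to 8% of events resolved after the limit. The median moved by at most 0.04 month.

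**The case against.** The strongest reply is that *unresolved* may mean unresolved at the censoring date. Later end dates would then be ignored, the common-stop rule would already be in force, and this bias would be absent. The SAP does not rule that out, and nowhere does it say that late resolutions are counted. But it does not state that meaning either, and the Appendix A rule on missing stop dates fits the literal coding. Two programmers could draw different curves from the same sentence.

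Other points stand:

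- Section 5 names no time-to-resolution output. It lists durations, which Section 3 defines for resolved events only. A curve follows only from the general Kaplan-Meier sentence. Against that, time to resolution is the one adverse-event timing variable in Section 3 with a censoring rule, which has no purpose unless a censored analysis is run.
- The analysis is descriptive, with no hypothesis test.
- The SAP pools three studies. The protocol speaks for 20210004 only, and the other protocols and individual SAPs were not available.
- For 20210004 the limit matches the end of the safety follow-up window, so having a limit is reasonable. The fault is that it applies to one kind of event only.

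A reader might also infer that the protocol follows every event until it resolves. It does not: stabilization, another explanation or loss to follow-up also ends follow-up. The argument needs only that some end dates after the limit are recorded.

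**Conclusion.** The concern holds as a fault in the rule read literally: after the limit the risk set contains only events already known to resolve, and any Kaplan-Meier estimate of time to resolution is too high in its late part. It does not hold as proof that a reported curve will be biased, because that depends on how *unresolved* is coded and on whether a curve is produced.

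The size cannot be derived from the documents. Under the assumed inputs it is 0.1 point or less for short cycle 1 events, so CRS is essentially unaffected. It is a few points for moderately slow events spread over treatment, and more than 10 points for slow events that start around the last dose or are viewed at 12 months. No single figure should be quoted as the bias of this plan.

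A reader might infer that median time to resolution is generally understated. The checks do not support that: in the mixtures the median hardly moved. A clear shift appeared only in the most extreme scenario (onset around last dose, m = 90, p = 0.2). There the true median solves 0.8 × (1 − 2^(−t/90)) = 0.5, so t = 90 × log2(1/0.375) ≈ 127 days, while the literal curve had already passed 50% by day 90.

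**What to change.** Use one stop for all events: the earliest of last dose + 65 days, end of study, death and analysis cutoff. Count a resolution only if the event's end date is on or before that stop; otherwise censor at the stop. Keep death in the list so that nobody remains at risk after dying. Name the Section 5 output that uses the variable. State also that events starting after the stop, which Period 4 can include, are left out of it; the present wording would give them a negative time.

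The cost is one sentence and one line of derivation code, with no new data. The downside is that late resolutions become censored, so the late part of the curve is less precise or not estimable. In the scenarios with onset around the last dose, no event was left at risk at day 180 under the common stop.

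Dropping the limit and censoring at the last known status date is less safe. Follow-up may end at stabilization, and stabilized events may be less likely to resolve, so that rule can also censor informatively. The full-follow-up checks above had only death and cutoff as censoring and do not test it.
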